3.5 Discontinuation of Subjects following any Treatment with Study Drug

Subjects **MUST** discontinue investigational product (and non-investigational product at the discretion of the investigator) for any of the following reasons:

- Subject's request to stop study treatment
- Any clinical adverse event (AE), laboratory abnormality or intercurrent illness which, in the opinion of the investigator, indicates that continued participation in the study is not in the best interest of the subject
- Termination of the study by Bristol-Myers Squibb (BMS)
- Loss of ability to freely provide consent through imprisonment or involuntarily incarceration for treatment of either a psychiatric or physical (eg, infectious disease) illness
- Unblinding a subject for any reason (emergency or non-emergency)
- Use of prohibited medication
- Missed two or more doses of investigational product for any reason during the Double Blind Period

In the case of pregnancy, the investigator must immediately notify the BMS Medical Monitor/designee of this event. In the event a normal healthy female becomes pregnant during a clinical trial, the study drug must be discontinued immediately. In most cases, the study drug will be permanently discontinued in an appropriate manner (eg, dose tapering if necessary for subject safety). Please call the BMS Medical Monitor within 24 hours of awareness of the pregnancy. If the investigator determines a possible favorable benefit/risk ratio that warrants continuation of

study drug, a discussion between the investigator and the BMS Medical Monitor/designee must occur.

All subjects who discontinue study drug should comply with protocol specified follow-up procedures as outlined in [Section 5](#). The only exception to this requirement is when a subject withdraws consent for all study procedures including post-treatment study follow-up or loses the ability to consent freely (ie, is imprisoned or involuntarily incarcerated for the treatment of either a psychiatric or physical illness).

If study drug is discontinued prior to the subject's completion of the study, the reason for the discontinuation must be documented in the subject's medical records and entered on the appropriate case report form (CRF) page.

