4.5.4.2 Dose Modifications Due to an Adverse Event

If there is evidence of toxicity in abnormal laboratory tests or clinical adverse events that, in the judgment of the Investigator, could place the subject at increased risk, study drug administration should be interrupted and the investigator should notify BMS. Subjects may be considered eligible to receive further study medication treatment only if full resolution of the adverse event is documented. Under no circumstances should the dose of study drug be altered due to an adverse event.

The IV infusion dosing window may be extended if the delay is due to an adverse event and if the adverse event has completely resolved. For Day 15, the dose may be delayed up to 7 days. For all subsequent IV infusions, the dose may be delayed up to 14 days. If the adverse event has not resolved within these windows, the IV infusion scheduled for that visit should be skipped (missed one IV dose). For example, if the Day 57 dose could not be administered until the 73rd day, the Day 57 dose should be skipped and the subject's next dose would occur at the Day 85 visit. Only two missed doses are allowed in the Double Blind Period.

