6 STUDY PERIODS, TREATMENT REGIMENS AND POPULATIONS FOR ANALYSES

6.1 Study Periods

In this study, there are four study periods: screening period, double-blind period (DB), open label extension period (OLE), and follow-up period.

The following analysis periods defined below are for analysis purposes. The definitions below indicate the data to be included in the analysis of each specified period. Subjects discontinued during a specified period (DB or OLE) will be considered on-treatment for 56 and 42 days after the last dosing in that period for safety and efficacy analysis respectively. Follow-up period data will be included in one of the analysis periods depending on the time of completing the study.

Screening Period: Starts with the day of enrolment and ends prior or on the day of first dose of study medication (abatacept or placebo).

Double-Blind Period: Starts with the first dosing of double-blind study medication and ends 56/42 days (for safety/efficacy analysis) after the last dose of the double-blind period or the first dosing of OLE, whichever is earlier.

For subjects who completed Period 1 and entered Period 2 prior to Protocol Amendment 2, includes data from first dose date in Period 1 up to the first dose in Period 2.

Open Label Extension Period (OLE): Starts with the first dosing in the OLE and ends 56/42 (for safety/efficacy analysis) days after the last dose in the OLE.

Cumulative Abatacept Safety Period: Starts at the time of the first dose of abatacept (either in the double-blind period for the subjects randomized to abatacept or in the OLE for the subjects randomized to placebo) and continues up to 56 days post last dose of abatacept for safety (AE and laboratory summaries). The last abatacept dose can be last dose in double-blind period for subjects not treated in the OLE.

For subjects who completed Period 1 and entered Period 2 prior to the protocol revision:

- For subjects on abatacept during Period 1:
 - For subjects who do not enter OLE period: starts with the first dosing of Period 1 and ends 56 days after the last dosing of Period 1.
 - For subjects who enter OLE period: starts with the first dosing of Period 1 and ends 56 days after the last dosing of Period 1 combined with OLE period that starts with the first dosing in the OLE period and ends 56 days after the last dosing in the OLE period.
- For subjects on placebo during Period 1:

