8.6 Day Ranges for Analysis Time Points

Subjects do not always adhere strictly to the visit schedule timing in the protocol. Therefore the designation of visits during treatment will be based on the day of evaluation relative to the study (day of first infusion = study Day 1) rather than the nominal visit recorded in the case report form (CRF). Mutually exclusive relative day windows are defined in the following table to provide derived visits that correspond to the post-baseline time points specified in the protocol.

Designation of visits for efficacy assessments and outcomes research performed at every scheduled visit is tabulated in [Table 8.6-1](#).

Table 8.6-1: Day Ranges for Components of Renal Response, Component of Completed Remission and Outcomes Research Assessments at Every Scheduled Visit During the Double-Blind Period and OLE Period

Visit	Target Day	Component of Renal Response/ Complete Remission (UPCR, eGFR)	eGFR (Provided by Lab)	Outcomes Research Day Ranges
Double-blind period				
Screening	< 1	< 1	< 1	< 1
Day 1 (Baseline)	1	1	1	1
Day 15	15	8 - 22		
Day 29	29	23 - 43		
Day 57	57	44 - 71		
Day 85	85	72 - 99		2 - 99
Day 113*	113	100 - 127	50 - 177	100 - 127
OLE period				
Day 141	141	128 - 155		
Day 169	169	156 - 183		
Day 197	197	184 - 211		
Day 225	225	212 - 239		
Day 253	253	240 - 267		
Day 281	281	268 - 295		

* Day 113 assessment for subjects continuing in OLE, the upper inclusive limit of this window is the first infusion in OLE or 42 days after last dose in double-blind period, whichever comes earlier. Assessments within 42 days after last dose in double-blind period are included for subjects discontinuing during double-blind period.

For subjects who completed Period 1 and entered Period 2 prior to the protocol revision:

Table 8.6-2: For Subjects who Completed Period 1 and Entered Period 2 prior to the Protocol Revision

Visit	Target Day	Component of Renal Response/ Complete Remission (UPCR, eGFR)	eGFR (Provided by Lab)	Outcomes Research Day Ranges
Double-blind (Period 1 and Period 2)				
Screening	< 1	< 1	< 1	< 1

Table 8.6-2: For Subjects who Completed Period 1 and Entered Period 2 prior to the Protocol Revision

Visit	Target Day	Component of Renal Response/ Complete Remission (UPCR, eGFR)	eGFR (Provided by Lab)	Outcomes Research Day Ranges
Day 1 (Baseline)	1	1	1	1
Day 15	15	8 - 22		
Day 29	29	23 - 43		
Day 57	57	44 - 71		
Day 85	85	72 - 99		2 - 99
Day 113*	113	100 - 120	50 - 141	100 - 127
Day 128	128	121 - 134		

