Day 141	141	135 - 155		
Day 169	169	156 - 183-	142 - 183	
Day 197	197	184 - 211	184 - 211	
Day 225*	225	212 - 239	212 - 239	
OLE period				
Day 253	253	240 - 267		
Day 281	281	268 - 295		
Day 309	309	296 - 323		
Day 337	337	324 - 351		
Day 365	365	352 - 379		
Day 393	393	380 - 407		

* Day 113 assessment for subjects continuing in Period 2, the upper inclusive limit of this window is the first infusion in Period 2 or 42 days after last dose in Period 1, whichever comes earlier. Day 113 assessment extends 42 days after last dose in Period 1 for subjects discontinuing during Period 1. Similarly, Day 225 assessment for subjects continuing in OLE, the upper inclusive limit of this window is the first infusion in OLE or 42 days after last dose in Period 2, whichever comes earlier. Assessments within 42 days after last dose in Period 2 are included for subjects discontinuing during Period 2.

Table 8.6-3: Day Ranges for Laboratory Assessments at Every Scheduled Visit During the Double-Blind Period and OLE Period

Visit	Target Day	Chemistry	CBC	Total Cholesterol and Triglycerides, fasting
Double-blind period				
Screening	< 1	< 1	< 1	< 1
Day 1 (Baseline)	1	1	1	1

Table 8.6-3: Day Ranges for Laboratory Assessments at Every Scheduled Visit During the Double-Blind Period and OLE Period

Visit	Target Day	Chemistry	CBC	Total Cholesterol and Triglycerides, fasting
Day 15	15	8 - 22		
Day 29	29	23 - 43	15 - 57	
Day 57	57	44 - 71		28 - 56
Day 85	85	72 - 99	58 - 99	
Day 113*	113	100 - 141	100 - 197	57 - 197
OLE period				
Day 169	169	142 - 197		
Day 225	225	198 - 253		
Day 281	281	254 - 309	198 - 309	198 - 309

* Day 113 assessment for subjects continuing in OLE, the upper inclusive limit of this window is the first infusion in OLE or 42 days after last dose in double-blind period, whichever comes earlier. Assessments within 42 days after last dose in double-blind period are included for subjects discontinuing during double-blind period.

For subjects who completed Period 1 and entered Period 2 prior to the protocol revision:

Table 8.6-4: For Subjects who Completed Period 1 and Entered Period 2 prior to the Protocol Revision

Visit	Target Day	Chemistry	CBC	Total Cholesterol and Triglycerides, fasting
Double-blind (Period 1 and Period 2)				
Screening	< 1	< 1	< 1	< 1
Day 1 (Baseline)	1	1	1	1
Day 15	15	8 - 22		
Day 29	29	23 - 43	15 - 57	
Day 57	57	44 - 71		28 - 56
Day 85	85	72 - 99	58 - 99	
Day 113*	113	100 - 120	100 - 141	57 - 169
Day 128	128	121 - 134		

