For subjects who discontinue from study therapy prematurely, assessments performed after the last infusion of study drug will be included in the efficacy and safety data sets provided that these assessments are made within 42 and 56 days respectively of the last infusion.

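### For completers who skip only the Day 85 infusion, the 42-day cap shuts out the Day 113 assessment, so an observed response is scored as failure

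*SAP*

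**What the plan says.** **Day 113 window.** SAP Table 8.6-1 sets Days 100 to 127 for UPCR and eGFR as response components and for PROMIS, and Days 50 to 177 for laboratory-provided eGFR. Table 8.6-3 sets Days 100 to 141 for chemistry, which includes albumin. For OLE entrants the footnotes to both tables add that the "upper inclusive limit of this window is the first infusion in OLE or 42 days after last dose in double-blind period", taking the earlier date.

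**Period definition.** SAP 6.1 says that the double-blind period "ends 56/42 days (for safety/efficacy analysis) after the last dose of the double-blind period or the first dosing of OLE, whichever is earlier". For pre-amendment subjects who went on to Period 2, the same section "includes data from first dose date in Period 1 up to the first dose in Period 2". The footnotes to Tables 8.6-2 and 8.6-4, however, say for those subjects that the "upper inclusive limit of this window is the first infusion in Period 2 or 42 days after last dose in Period 1", again whichever is earlier.

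**Who the 42 days are for.** SAP 6.1 introduces them this way: "Subjects discontinued during a specified period (DB or OLE) will be considered on-treatment for 56 and 42 days after the last dosing". SAP 8.6 closes in the same vein: "For subjects who discontinue from study therapy prematurely, assessments performed after the last infusion of study drug will be included in the efficacy" data if made within 42 days of that infusion. SAP 7.4.2 treats a subject as discontinued from a period only if the subject status page shows non-completion.

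**Missed doses.** Protocol 3.5 requires discontinuation for "Missed two or more doses of investigational product for any reason during the Double Blind Period". Protocol 4.5.4.2 foresees a single omission: if an adverse event outlasts the permitted delay, "the IV infusion scheduled for that visit should be skipped (missed one IV dose").

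**Missing data.** SAP 7.5.1 and 8.2 count a missing Day 113 response, or any missing component, as non-response.

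**The concern.** The cap suits a fully dosed subject: 85 + 42 = Day 127, the upper limit in the table. It fails when Day 85 is the one dose skipped, because the clock then starts from the Day 57 dose. The subject has completed the period, belongs to the ITT population and has been assessed at the scheduled visit, yet the assessment maps to no double-blind time point and the missing-data rule supplies a failure.

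All four secondary efficacy endpoints lose the same visit. Complete remission is scored as failure, and the Day 113 UPCR, albumin and PROMIS values drop out.

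Nothing planned would expose this. The per-protocol set excludes subjects only for two or more missed doses (SAP Appendix 2, Relevant Protocol Deviations). The sensitivity analysis in SAP 7.5.2 only drops the genotype factor. If skipping differs between arms, the treatment difference can shift in either direction.

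**Working it through.** **1. Inputs.** Double-blind doses fall on Days 1, 15, 29, 57 and 85 (protocol 4.5.2). From Day 57 on, the ordinary dosing window is ±7 days (4.5.4.1), and a dose may be delayed by up to 14 days for an adverse event (4.5.4.2). OLE Day 1 is double-blind Day 113 (3.1.3).

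**2. Window for an OLE entrant who skips only Day 85.** Upper limit = min(127, day of last double-blind dose + 42, day of first OLE infusion). The lower limit stays at Day 100.

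| Day 57 dose given on | Cap | UPCR/eGFR window | Day 113 visit |
|---|---|---|---|
| Day 50 | 92 | empty | out |
| Day 57 | 99 | empty | out |
| Day 58 | 100 | Day 100 only | out |
| Day 64 | 106 | Days 100–106 | out |
| Day 70 (adverse-event delay) | 112 | Days 100–112 | out |
| Day 71 (latest allowed) | 113 | Days 100–113 | in |

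The window is empty for doses on Days 50 to 57. It opens briefly for doses on Days 58 to 70, but still excludes a Day 113 visit. The PROMIS and chemistry windows also open on Day 100 and fail in the same way. After a nominal Day 57 dose the laboratory eGFR window shrinks to Days 50 to 99, while scheduled double-blind eGFR is only on Days 1 and 113 (protocol Table 5.1-2). Losing UPCR alone is already enough for non-response.

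The visit itself may move by ±7 days. For dose days 50–64 and visit days 106–120 there are 15 × 15 = 225 date pairs. Only one satisfies visit ≤ dose + 42 (dose Day 64, visit Day 106). With dose days extended to 71 there are 22 × 15 = 330 pairs, and 1 + 2 + … + 8 = 36 are kept. These are counts of dates, not probabilities.

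**3. Other completers.** For those who do not enter the OLE, the SAP 6.1 definition ends efficacy data at the same last dose + 42. For Period 1 completers, the UPCR window in Table 8.6-2 and the chemistry window in Table 8.6-4 are Days 100 to 120, so a cap at Day 99 empties both.

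**4. The plan's power figure.** SAP section 5 states about 80% for 45 per arm, 40% vs 12%, two-sided 5%. The continuity-corrected normal formula gives Φ[(0.28 − 1/45 − 1.96 × √(2 × 0.26 × 0.74/45)) / √((0.40 × 0.60 + 0.12 × 0.88)/45)] = Φ[(0.2800 − 0.0222 − 0.1812)/0.0876] = 80.9%, so the figure reproduces. Exact enumeration with Fisher's test gives 82.1%. Fisher is used below as a simple stand-in for the planned logistic model.

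**5. Size per subject.** 1/45 = 2.2 points. Near the planned rates, 18 vs 5 responders gives Fisher p = 0.003 and 17 vs 5 gives 0.006. At the margin, 14 vs 5 gives 0.037 and 13 vs 5 gives 0.063.

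**6. Size under assumed skipping.** Let s be the share skipping Day 85 and r their response relative to other subjects. Both are assumptions. Rate without cap = p(1 − s + sr); with cap = p(1 − s); expected responders rescored per arm = 45spr.

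- s = 2% in both arms, r = 1: 39.2% vs 11.76%; power 82.1% → 80.9%.
- s = 5% in both arms, r = 1: 38.0% vs 11.4%; rescored 0.9 and 0.27; power 82.1% → 79.0%.
- s = 5% in both arms, r = 0.5: power 80.6% → 79.0%.
- r = 0: the cap costs nothing.
- s = 5% in the abatacept arm only, r = 1: difference 38.0 − 12.0 = 26.0 points instead of 28.0.
- s = 5% in the placebo arm only, r = 1: 40.0 − 11.4 = 28.6 points.

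**The case against.** The best defence is that this is a deliberate on-treatment rule. It matches the table for full dosing, SAP 6.1 applies it to the whole double-blind period, and SAP 8.2 calls its handling of discontinuations conservative. Whether a value taken 56 days after the last dose should count is partly an estimand choice.

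That choice is open to the sponsor, but the SAP does not state it. The 42 days are introduced, and repeated at the end of 8.6, for subjects who discontinue; SAP 7.4.2 makes these subjects completers; and the analysis is ITT. Protocol 8.4.2.1 imputes failure to those who stop before Day 113, not to those assessed on that day. The antibody footnote to Table 8.6-5 uses 56 days: 57 + 56 = 113, so at the same nominal visit the antibody sample counts and the primary endpoint does not.

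The points on size do stand. The group is narrow: the Day 85 dose may be given up to Day 92 routinely, or Day 99 after an adverse event (cap Day 141), without any harm. No skip rate is given, and 14 vs 5 is a deliberately marginal example. For UPCR and albumin the mixed model keeps the subject's earlier visits, so one value is lost and not the subject.

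**Conclusion.** The point holds as a drafting fault with a definite effect on each subject it reaches. On the protocol schedule, a completer who skips only Day 85 has the Day 113 result excluded, and any observed renal response or complete remission becomes a failure. The dates follow from the documents alone. The power and bias figures rest on assumed skip rates and on how skippers respond; the overall effect is probably small.

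Four stronger inferences are not supported:

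- A reader might infer that completers who do not enter the OLE are left without a rule, since the Table 8.6-1 footnote does not name them. SAP 6.1 does cap them.
- A reader might see a flat contradiction for Period 1 completers. A visit window can be narrower than its period, so both rules can be applied. It is an inconsistency that should be aligned.
- A reader might include pediatric early escapers, who also enter the OLE without a Day 85 dose. They leave the double-blind period at about Day 85 and have no double-blind Day 113 assessment to discard. They are taken here as discontinuations, which are non-responders in any case.
- A reader might conclude that the primary result is materially biased. Without a skip rate by arm, neither the size nor the direction can be stated.

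**What to change.** Limit the change to the Day 113 efficacy assessment. In the SAP 6.1 double-blind efficacy definition, and in the Day 113 part of the footnotes to Tables 8.6-1 to 8.6-4, state:

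> For the Day 113 assessment, the 42-day limit applies only to subjects who did not complete the double-blind period (or Period 1) per the subject status CRF page. For completers, the Day 113 value is the assessment closest to Day 113 within the tabulated window and no later than the pre-dose sample on the day of the first OLE (or Period 2) infusion. For all completers, eGFR for renal response and complete remission uses the same Day 113 window as UPCR.

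The last sentence stops the change from admitting eGFR values out to Day 177 and gives all completers one eGFR rule, whether or not they enter the OLE. Leave the 42-day limits for the OLE and for Period 2/Day 225, and the 56-day safety limits, as they are. A general statement that the 42 days apply only to non-completers would remove those as well.

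The cost is a few lines, best written before unblinding, with no new data. The downside is that a few Day 113 values come about 113 − 57 = 56 days or more after the last dose. For OLE or Period 2 entrants the first infusion of that period still closes the window. For completers who do not enter the OLE, after a nominal Day 57 dose, the outer limits are 127 − 57 = 70 days for UPCR and eGFR and 141 − 57 = 84 days for albumin. The closest-to-target rule makes those extremes unlikely. If the sponsor does intend an on-treatment rule for completers, the SAP should say so and justify it.

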Study Drug for IM101566		
Medication	Potency	IP/Non-IP
Intravenous Abatacept	10 mg/kg	IP

Study Assessments: The primary outcome used will be a composite renal index which will be used to determine the rate of renal responders. Secondary endpoints will be determined by assessing complete remission (defined as UPCR \leq 0.3 with preservation of eGFR), the change in patient reported outcomes (using PROMIS measures), change in height as determined by standard deviation score (HSDS; z-scores) for subjects < 18 years and laboratory assessments (serum albumin, serum total cholesterol and triglycerides).

Statistical Considerations:

Sample Size: The study is planned to randomize 90 subjects to assess the primary endpoint of proportion subjects in Renal Response at Day 113 between the IV Abatacept and placebo arms. The randomization will be stratified by Genotype (*APOLI* high risk group vs Others) and Age (< 18 and \geq 18).

Endpoints:

Primary Endpoint: The primary efficacy endpoint is the proportion of subjects in Renal Response at Day 113.

Secondary Efficacy Endpoint(s):

- Mean change from baseline in UPCR at Day 113
- Mean change from baseline in serum albumin at Day 113
- Proportion of subjects achieving complete remission (UPCR \leq 0.3 with eGFR: normal or \geq 75% baseline if below normal at baseline) at Day 113
- Mean change from baseline in PROMIS measures at Day 113

Safety Endpoints:

- All adverse events (AEs, SAEs, AE leading to discontinuation, deaths)
- AEs of interest (infections, malignancies, autoimmune disorders, infusional related reactions, renal-related events)
- Laboratory test abnormalities

Immunogenicity Endpoint: Proportion of subjects with positive antibody response relative to baseline over time.

[REDACTED]

- [REDACTED]
- [REDACTED]

Analyses:

Summary of Planned Efficacy Analyses	
Measure of Interest	Analysis Method
Renal Response	Primary Analysis: Using a logistic regression model that includes treatment arm, randomization stratification factor (Genotype, Age) and baseline UPCR as continuous variable and point estimate of adjusted ORs, corresponding 95% CI and p-value will be provided.

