4.5.2 Administration of Abatacept or Placebo

The Central Randomization System will confirm the subject's body weight and age and assign the number of vials of abatacept to allocate for the visit. Subjects will receive doses of study medication at every treatment period visit (Days 1, 15, 29, 57 and 85 during Double Blind Period).

Subjects who are randomized to receive placebo will be given either Dextrose 5% in Water (D5W) or Normal Saline (NS) at the discretion of the investigator. Placebo (NS or D5W) will be supplied by the investigative site.

A ± 3 day window is allowed for the dose on Day 15, a -3 and +7 day window is allowed for the dose on Day 29 and a ± 7 day window is allowed for doses thereafter. Infusions should occur at approximately the same time of day throughout the duration of the study.

All doses of study medication will be administered intravenously in a fixed volume of 100 ml at a constant rate of flow over approximately 30 minutes. Please flush with D5W or NS at the end of the infusion to ensure that the administration line used to deliver the drug solution is adequately cleared; please refer to the infusion set's manufacturer's materials to determine the appropriate flush volume needed to assure delivery of the entire dosage. The infusion solution must be prepared by a qualified staff member and supplied to personnel administering the dose in a container not identifying the contents so as to maintain the blind. The infusion of the fully diluted abatacept/placebo must be completed within 24 hours of reconstitution of the vials. The fully diluted abatacept/placebo may be stored at room temperature or refrigerated at 2°C to 8°C (36°F to 46°F) before use. The fully diluted solution should be discarded if not administered within 24 hours.

All intravenous infusions will be with the subject in the seated position. No adjustments will be made in treatment dose level or schedule. Subjects will be observed for adverse events and vital signs (seated blood pressure, heart rate, and temperature) from the start of each infusion (pre-dose and 60 minutes). There is a ± 5 -minute window for vital sign collection. Subjects will be observed for a minimum of 1 hour from the start of the infusion. The observation period should be extended if clinically indicated.

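### The SAP's Day 57 window for cholesterol and triglycerides (Days 28–56) leaves out Day 57 itself, so an on-time sample is assigned to Day 113 in the by-visit lipid summaries

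*SAP*

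**What the plan says.** SAP Section 8.6 places each assessment by its study day, "rather than the nominal visit recorded in the case report form (CRF". It adds: "Mutually exclusive relative day windows are defined in the following table". A sample can therefore belong to one window only. If a window holds several samples, the one nearest the target day is used.

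The laboratory windows are in Table 8.6-3, with a parallel Table 8.6-4 for subjects who entered Period 2 under the previous design. The columns of both are "Visit Target Day Chemistry CBC Total Cholesterol and Triglycerides, fasting". The rows at issue are:

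- Day 57, printed the same in both tables: "Day 57 57 44 - 71 28 - 56". The CBC cell is empty, so the last range is the lipid one.
- Day 113 in Table 8.6-3: "Day 113* 113 100 - 141 100 - 197 57 - 197".
- Day 113 in Table 8.6-4: "Day 113* 113 100 - 120 100 - 141 57 - 169".

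The Day 113 footnotes cap only the upper end of that window, at the first infusion of the next period or 42 days after the last double-blind (or Period 1) dose.

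For timing, Protocol Section 4.5.2 sets separate windows for the Day 15 and Day 29 doses. For later doses a ±7 "day window is allowed for doses thereafter".

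**The concern.** A visit window should contain the day it is built around. Here the lipid window for Day 57 ends the day before its target, and the target day opens the next window. Since the derived visit overrides the CRF label, nothing returns the sample to Day 57.

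SAP Section 7.6.5 summarizes laboratory values and their changes from baseline by study day and treatment group. Programmed as written, the Day 57 lipid row would hold only samples taken before Day 57. The Day 113 row could hold eight-week values from subjects with no later sample. Neither row would then reliably describe the time point it names.

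**Working it through.** **1. Is the column read correctly?** In Table 8.6-3 the CBC ranges run 15–57, 58–99, 100–197, 198–309. The lipid ranges run 28–56, 57–197, 198–309. Each sequence is continuous, so 28–56 belongs to lipids and is not a displaced CBC entry.

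**2. Does each window contain its target?** For lipids at Day 57, 57 > 56, so it does not. Day 57 lies in 57–197 (Table 8.6-3) and in 57–169 (Table 8.6-4), so it is assigned to Day 113. Every other chemistry, CBC and lipid window in the two tables contains its target day. In the same row, chemistry does: 44 ≤ 57 ≤ 71.

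**3. What rule do the other limits follow?** The SAP states none, but the printed limits match midpoints between adjacent target days, with the midpoint day given to the earlier visit:

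| Column | Adjacent targets | Midpoint | Printed cut |
|---|---|---|---|
| Chemistry | 15, 29 | (15+29)/2 = 22 | 22/23 |
| Chemistry | 29, 57 | (29+57)/2 = 43 | 43/44 |
| Chemistry | 57, 85 | (57+85)/2 = 71 | 71/72 |
| Chemistry, CBC | 85, 113 | (85+113)/2 = 99 | 99/100 |
| CBC | 29, 85 | (29+85)/2 = 57 | 57/58 |
| CBC, lipids (8.6-3) | 113, 281 | (113+281)/2 = 197 | 197/198 |
| Lipids (8.6-4) | 113, 225 | (113+225)/2 = 169 | 169/170 |
| **Lipids, both tables** | **57, 113** | **(57+113)/2 = 85** | **56/57** |

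Of the cuts between neighbouring post-baseline visits, only the lipid cut between Day 57 and Day 113 departs from this pattern. The lower limit of 28 is also one day below the midpoint with baseline, (1+57)/2 = 29, which is harmless.

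**4. Size in calendar days.** If the ±7-day dosing window governs sampling, Day 57 may be sampled on Days 50–64, which is 15 days. Days 50–56 (7 days) map to Day 57. Days 57–64 (8 days, including the target) map to Day 113.

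**5. What happens to the misassigned sample?**

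- *A sample nearer Day 113 exists.* A Day 57 sample is 113 − 57 = 56 days from target, and one taken on Day 113 is 0 days away. The later sample is used, and the Day 57 value appears in neither by-visit row.
- *No nearer sample exists.* The Day 57 value becomes the Day 113 value. The post-discontinuation limits (42 days after the last infusion for efficacy, 56 for safety) do not prevent this. A subject last dosed on Day 29 is only 57 − 29 = 28 days past that dose.

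**6. Exact attendance.** If all subjects are sampled on Day 57, none falls in 28–56 and the Day 57 lipid row is empty in both arms.

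**The case against.** The slip itself is hard to dispute, but its reach is limited.

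*Lipids as a secondary endpoint.* The synopsis describes the secondary assessments as including "laboratory assessments (serum albumin, serum total cholesterol and triglycerides", and a reader might infer that a secondary endpoint is damaged. The documents do not support that. The secondary efficacy lists in the synopsis, Protocol Section 8.3.2.1 and SAP Section 4.2 contain UPCR, albumin, complete remission and PROMIS, and no lipids. Protocol Section 3.1 introduces the corresponding list as covering secondary and exploratory endpoints together. Exploratory text is blacked out, so the only readable use of lipids is the by-study-day laboratory summary. Marked-abnormality counts are taken over the treatment period and do not depend on visit windows.

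*Contamination of Day 113.* A reader might infer that early leavers routinely put eight-week values into the Day 113 row. That happens only when no sample nearer Day 113 exists. Protocol Section 5.2 asks subjects who stop early to complete an Early Termination visit; a lipid sample taken then, after Day 57 and before Day 113, would be nearer and would be chosen. Table 8.6-4 covers only subjects who completed Period 1, so there the problem needs a missing sample.

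*Loss of data.* A reader might take the Day 57 value to be deleted. It leaves the by-visit summary; nothing says it leaves the database.

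*The 8 of 15.* This counts calendar days, not subjects, and borrows a dosing window. It is not a misclassification rate.

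All four limits stand. None of them puts Day 57 back into the Day 57 window.

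**Conclusion.** The lipid windows are wrong as written in both tables: a sample taken on schedule at Day 57 is assigned to Day 113. With exact attendance the Day 57 lipid row is empty. With sampling allowed ±7 days, on-time and late samples (Days 57–64) are misassigned and only early ones (Days 50–56) stay. The share of subjects affected depends on attendance, which the documents cannot give.

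The consequence is confined to by-visit cholesterol and triglyceride summaries. UPCR and eGFR, and so renal response and complete remission, use Tables 8.6-1 and 8.6-2. Albumin follows the chemistry column, whose Day 57 window is sound. This is a minor correction, worth making before the tables are programmed. It rests on Day 57 being a planned lipid visit, which the SAP tables themselves show, and on the ±7-day window only for the day count.

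**What to change.** In the lipid column of Tables 8.6-3 and 8.6-4, set Day 57 to 28–85 and start Day 113 at Day 86: 86–197 in Table 8.6-3 and 86–169 in Table 8.6-4. Leave the upper limits and footnote caps alone. This follows the tables' own practice of giving the midpoint day to the earlier visit, and puts all of Days 50–64 in the Day 57 window.

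The edit is four numbers, with one small downside. Early Termination lipid samples from Days 57–85, which now fall under Day 113, would move to the Day 57 window, where the scheduled Day 57 sample would usually be preferred. That includes a pediatric early-escape visit on Day 85, which Protocol Table 5.1-2 treats as Early Termination. Cutting at 84/85 instead (28–84, then 85 onward) keeps a Day 85 sample in the Day 113 row and also cures the defect, at the price of departing from the midpoint convention by one day. The sponsor should choose between the two cuts and record the choice before unblinding.
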